Number of Sites:	A minimum of 10 study sites will participate. Any one site may not enroll more than 40 Subjects (inclusive combination of both THA and hemi-hip arthroplasty Subjects) after reallocation from low enrollment sites, which will ensure that in a worst-case scenario, a minimum of 4 sites must contribute enrollment to the final sample size to represent variability across surgeons.	
Subject Population:	Subjects at participating sites who meet the inclusion/exclusion criteria for this study.	
Sample Size:	Sites will prospectively enroll a total of 255 Subjects to include a minimum of 225 Primary THA Subjects, and a cohort of a minimum of 30 hemi-hip arthroplasty Subjects.	
	The anticipated duration of this investigation is approximately 3- to 4-years from the time of study initiation given that:	
Study Duration:	• It may take up to 1-year from the time of study initiation to enroll total hip arthroplasty Subjects. It is expected that the hemi-hip arthroplasty cohort may take longer than 1-year to enroll.	
	Each Subject will be followed until they have completed their minimum 2-year follow-up.	
	• The study will be closed when all Subjects have completed minimum 2-year follow-up.	

Table 2 Study Summary		
Title:	Actis® Total Hip System 2-Year Follow-up	

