#### 8.1 Duration of Study

The estimated duration of the overall clinical study is 3-years: 1-year for enrollment and 2-years for postoperative follow-up. Although, it is expected that the hemi-hip arthroplasty cohort may take longer than 1-year to enroll. At the minimum 2-year visit, an End of Study eCRF will be completed for every study Subject who has not been prematurely withdrawn, and study participation will conclude.

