#### 10.3 Secondary Endpoints

- Harris Hip score at 3-months and 1-year
- Radiographic evaluation at 2-years postoperatively, inclusive of leg length discrepancy
- Type and frequency of AEs through 2-years postoperatively
- Device survivorship at 2-years postoperatively

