### 16.10 Analysis Plan

Results for the cohorts of Subjects who were enrolled with a primary THA, and who were enrolled with a primary hemi-hip arthroplasty procedure will be summarized side-by-side, and overall, unless otherwise stated. Demographics, baseline subject characteristics, procedure characteristics and the primary and secondary endpoints will be presented overall (pooled) and by study site. Descriptive statistics for dichotomous/categorical variables will include the number and percentage of subjects. For categorical endpoints, 2-sided 95% confidence intervals around observed percentages will be based on the binomial exact method. Descriptive statistics for continuous variables will include the number of subjects, mean, standard deviation, median, minimum, and maximum. For continuous endpoints, 2-sided 95% confidence intervals around the mean will be computed using the t-distribution.

CONFIDENTIAL Page 41 of 53
Version Date: May 7, 2018

DePuy Synthes / Actis® Total Hip System
Protocol #14014 / Version B

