- Radiographic measurements will provide True LLD by measuring each leg to the nearest millimeter. A LLD of 3 cm or greater will be considered a true LLD. A McNemar's test of discordant pairs will be utilized to compare perceived vs. actual LLD before surgery, and also to compare perceived vs. actual LLD after surgery.
- o Analysis of Change (post-surgical pre- surgical) of True LLD: Compare the difference between the absolute true LLD before and after hip replacement surgery for those cases that had a true LLD prior to hip replacement surgery (using a definition of 3 cm or greater as the threshold). The analysis variable will be the absolute value of the difference between the right and left knee and a paired t-test will be used to assess this difference.
- Analysis of proportion of cases that have true LLD after surgery will be presented and this
  will be compared to the proportion that had true LLD prior to surgery; McNemar's test of
  discordant pairs will be conducted.
- The type and frequency of AEs through 2 years post-operatively will be presented in table form and via a listing. Frequencies and listing of AE's seriousness, severity, whether unanticipated, outcome, and treatment will also be presented.
- Device survivorship at 2 years post-operatively. Kaplan-Meier survivorship will be conducted with removal of any component, defined as revision, for any reason specifying the event of interest. Cases not revised will be censored at their date of last follow-up, death, or withdrawal from the study. Survivorship point estimates and 95% confidence intervals will be presented when 40 subjects are left being followed. Survivorship analysis is not planned for the cohort of hemi-hip subjects as the sample size is insufficient; however, a listing will be provided to present all subjects requiring removal of any component.
- Stem Revision at 2 years post-operatively.

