#### 25 STUDY SUMMARY STATEMENT

In summary, this study will provide 2-year safety and performance data and outcomes for the Actis® Total Hip System. For a given Subject, their study participation will end when they have reached the final endpoint; that is, each Subject will reach "end of study" when they have had the minimum 2-year clinical evaluation. For Subjects participating in the optional and parallel Patient Activity Tracking portion of the study (ActiTrakTM), their participation in that particular aspect of the study will be completed when they have 3-months of postoperative data collected.

CONFIDENTIAL Page 53 of 53
Version Date: May 7, 2018

DePuy Synthes / Actis® Total Hip System
Protocol #14014 / Version B

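### Section 16.12 ties the 2-year survivorship estimate to the moment when 40 subjects remain, so its time point is not fixed at 2 years and the rule cannot work by site

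*Combined protocol and SAP*

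**What the plan says.** Section 10.3 lists the endpoint as "Device survivorship at 2-years postoperatively". The two matching bullets in Section 16.12, one for removal of any component and one for removal of the stem, are also headed as 2-year results. The first sets the method: "Kaplan-Meier survivorship will be conducted with removal of any component, defined as revision, for any reason specifying the event of interest". Both bullets use the same censoring rule, "Cases not revised will be censored at their date of last follow-up, death, or withdrawal from the study", and the same reporting rule, "Survivorship point estimates and 95% confidence intervals will be presented when 40 subjects are left being followed". Neither names a study day at which the curve is read.

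Section 8.1 says how subjects leave: "At the minimum 2-year visit, an End of Study eCRF will be completed for every study Subject who has not been prematurely withdrawn". Section 25 agrees that a subject reaches the end of study "when they have had the minimum 2-year clinical evaluation". The schedule in Section 6 gives that visit a window of day 669 to day 1763.

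Section 16.10 adds that "the primary and secondary endpoints will be presented overall (pooled) and by study site". In the Number of Sites row of Table 2, "Any one site may not enroll more than 40 Subjects", and that limit counts THA and hemi-hip subjects together. Section 16.12 plans no survivorship analysis for the hemi-hip cohort, so the Kaplan-Meier analyses cover THA subjects only.

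**The concern.** The endpoint fixes a time and the reporting rule fixes a number remaining. The two agree only by coincidence, because the day on which 40 subjects are left depends on when sites schedule the last visit. Two analysts could both follow Section 16.12 and report survivorship at different follow-up times under the same 2-year label.

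Section 8 names an estimate of device survivorship among the things the study is designed to provide. Few revisions are likely, so where the curve is read matters more than usual. In the tail, each event carries a large weight.

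The by-site requirement raises a second conflict. A rule that needs 40 subjects still in follow-up cannot be applied at a site that may not enroll more than 40 in total.

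**Working it through.** **Plan's own figure.** The plan states no precision or sample-size figure for survivorship. Its one computed design figure, in Section 16.9, is the margin of error on the mean Harris Hip Score: 1.96 × 10 / √200 = 1.39, which matches the stated 1.4. The expected 200 THA subjects with 2-year data, out of 225, are taken from there.

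**Inputs from the documents.** N = 200 THA subjects reaching the final visit (Section 16.9); exit at that visit (Sections 8.1 and 25); window day 669 to 1763, or 669/365.25 = 1.83 to 1763/365.25 = 4.83 years (Section 6); threshold 40 (Section 16.12).

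**Assumptions.** The documents give the window but not how visits fall within it, so several patterns are tried. Normal patterns are truncated to the window. For the size of the effect, a constant revision hazard with 98% survivorship at 2 years is assumed.

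**Formulas.** If F is the distribution of final-visit days:
- the day when 40 remain is the (1 − 40/N) quantile of F, here the 0.80 quantile;
- the number at risk at day 730 is N × (1 − F(730)), ignoring the few revisions;
- survivorship on day d is 0.98^(d/730.5).

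Example, visits uniform over the whole window: 669 + 0.80 × (1763 − 669) = day 1544, and 0.98^(1544/730.5) = 95.8%.

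| Assumed final-visit days | Day when 40 remain | Years | At risk at day 730 | Survivorship on that day | Gap from 98.0% (points) |
|---|---|---|---|---|---|
| Uniform 669–730 | 718 | 1.97 | 0 | 98.03% | −0.03 |
| Normal, mean 710, SD 20 | 727 | 1.99 | 32 | 98.01% | −0.01 |
| Normal, mean 730, SD 30 | 756 | 2.07 | 102 | 97.93% | 0.07 |
| Uniform 669–791 | 767 | 2.10 | 100 | 97.90% | 0.10 |
| Normal, mean 760, SD 45 | 799 | 2.19 | 153 | 97.82% | 0.18 |
| Uniform 669–1763 | 1544 | 4.23 | 189 | 95.82% | 2.18 |

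With N of 180 to 225 the day ranges from 716 to 1569. The share that must already have left for the rule to land on day 730 is 1 − 40/N: 78% at N = 180, 80% at 200, 82% at 225.

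**Simulation check.** Take 225 THA subjects, 25/225 = 11.1% lost early, and the same 98% assumption. The mean Kaplan-Meier estimate at 40 remaining against day 730 was 95.8% v 98.0% (uniform 669–1763), 97.9% v 98.0% (uniform 669–791) and 98.0% v 98.0% (normal, mean 710, SD 20). This agrees with the table. In the clustered patterns, doubling the revision rate roughly doubles the gap: at 96% survivorship the mean-760 pattern gives 0.96 − 0.96^(798.6/730.5) = 0.36 points.

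**Weight of one event.** With survivorship near 100%, one revision with 41 at risk lowers the estimate by about 1/41 = 2.4 points. With the 102 at risk at day 730 in the mean-730 pattern, it lowers it by about 1/102 = 1.0 point.

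**Who counts toward the 40.** Under Table 9, subjects with a liner-only or a cup-and-liner revision stay in follow-up, although they have already had the any-component event. The number still followed can therefore exceed the number at risk in that analysis.

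**By site.** The limit is 40 subjects, THA and hemi-hip combined. A site has 40 THA subjects still followed only if it enrolled 40 THA subjects and no hemi-hips, and only until its first subject leaves. With the planned 225 THA subjects and at least 10 sites, the average is at most 225/10 = 22.5 THA subjects per site.

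**The case against.** The strongest reply is that 40 is a display threshold. Both bullets are headed as 2-year results, and the hemi-hip cohort, planned at a minimum of 30, is excluded in the next sentence because its sample is too small. On that reading the plan gives a 2-year estimate whenever at least 40 subjects remain at risk. This is plausible, and it stands against a stronger conclusion that a reader might draw, namely that the planned figure is simply not a 2-year survivorship. The documents do not settle that. The sentence does not say that 40 is a minimum, but it does not rule it out either.

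Two other inferences also go too far. A reader might conclude that exit from day 669 makes a 2-year estimate impossible. It does not: early exits are censored, and four of the six patterns leave 100 or more at risk at day 730. The number falls below 40 only when most visits come before day 730. A reader might also conclude that the rule generally lands after 2 years. That rests on assumed visit timing, and two of the patterns put it slightly earlier.

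The objection is also right that the effect is small when visits cluster. The full-window pattern sits poorly with the overall duration of 3 to 4 years in Table 2 and 3 years in Section 8.1. The study has no control and no hypotheses, and Section 16.3 calls all analyses exploratory.

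What the objection does not remove is that the only stated rule is a count. Even as a display minimum, the text does not say what is reported if fewer than 40 remain at day 730. For by-site results, a display minimum would suppress essentially every site, which is sensible but contradicts Section 16.10.

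**Conclusion.** The concern holds in a limited form. Section 16.12 names 2-year endpoints but gives a reporting rule that, followed literally, reads the curve on a day set by visit scheduling. That day may fall before or well after 2 years: from 718 to 1544 with 200 subjects under the patterns tried. The documents support saying that the time point is not fixed. They do not support saying that the reported figure will necessarily differ from 2-year survivorship.

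The expected difference is about 0.2 points or less at 98% survivorship when visits cluster near 2 years, and about 2 points only when they spread over the whole window. These sizes rest on assumed visit distributions and an assumed constant revision rate, neither of which is in the documents.

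The by-site conflict needs no such assumption. It follows from Section 16.10 and the limit of 40 subjects per site.

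This should be corrected, because a stated rule conflicts with the endpoint it serves and the correction costs nothing in data.

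**What to change.** Change the wording of Section 16.12, with a matching exception in Section 16.10:

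- For both any-component and stem survivorship, state that the Kaplan-Meier estimate, its 95% confidence interval and the number at risk will be given at 2 years (day 730).
- Restate 40 as the minimum number at risk, so that the curve is not shown or interpreted beyond the point where fewer remain. Count subjects at risk for the event being analyzed, not all subjects still in follow-up.
- Say what will be reported at day 730 if fewer than 40 are at risk then.
- Replace by-site survivorship with the number revised and the number implanted at each site.

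The cost is SAP text only. No new data, visits or subjects are needed, and the dates required are already collected.

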# 16.13 Tertiary Endpoints

- Change in Subject Outcomes (*i.e.*, FJS-12, HOOS and Hip Evaluation) will be measured and compared from preoperative to 6 weeks, 3 months, minimum 1 year and minimum 2 years.
  - Raw measurements and change from baseline (pre-op) scores will be presented for FJS-12 and HOOS scores and will include number of subjects, mean, standard deviation, median, minimum, and maximum. Two-sided 95% confidence intervals around the mean will be computed using the t-distribution.
  - o Frequency tables will be provided for the following Hip Evaluation outcomes and include 2-sided 95% confidence intervals based on the binomial exact method: satisfaction, procedure again, and groin and buttock pain.
- Voluntarily participating study Subjects utilizing the wearable Patient Activity Tracking device and will provide the Sponsor with data on daily activity (*e.g.*, pain, location of pain, mood/emotion, activities of daily living and range of motion, and after surgery Subject satisfaction will be asked periodically) from the time of consent preoperatively (if possible) through 3 months postoperative.
  - The number of subjects participating, and the completeness and cleanliness of those data will impact analysis methods. At minimum, pain level before and after surgery will be summarized and presented by the corresponding category. Pain, location of pain, mood/emotion, activities of daily living, range of motion and Subject satisfaction will also be summarized.

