#### 10.4 Tertiary Endpoints

- Change in Subject Outcomes (*i.e.*, FJS-12, HOOS and Hip Evaluation) will be measured and compared from preoperative to 6-weeks, 3-months, minimum 1-year and minimum 2-years.
- Patient tracking activities reported from the mobile ActiTrakTM application will be analyzed for pain, location of pain, mood/emotion, and activities of daily living and range of motion. Subject Satisfaction will be asked periodically after surgery. The range of time for these tertiary endpoints will be from the time of consent preoperatively through 3-months postoperatively.

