#### 10.6 Optional (Electronic) Patient Activity Tracking Device

This clinical investigation will provide the opportunity for Subjects who are properly consented and deemed eligible for the study to join in a parallel and optional portion of the study – to electronically capture real-time patient activities of daily living (such as pain, location of pain, mood/emotion, activities of daily living and range of motion, Subject satisfaction will periodically be asked after surgery) from the time of consent preoperatively to 3-months postoperatively. If a Subject is unable or unwilling to provide the preoperative data, this will not preclude or delay them from enrollment. Subjects may also enroll in the Patient Activity Tracking on the day of their surgery and collect activities through the 3-month postoperative visit interval. This optional part of the study will be open for enrollment until 225 THA Subjects are treated; then, this part of the study will be closed. The fulfillment of 225 THA Subjects occurred June 5, 2017 and this portion of the study has now concluded with Version B of the protocol.

Patient Activity Tracking is a combination of a wearable watch-like device and a mobile application, specifically, the ActiTrakTM application. The wearable watch-like Patient Activity Tracking device will be linked (*i.e.*, electronically synced) to a downloaded mobile application (app) on the Subject's own well-functioning (and updated to the most current operating system version) smartphone. If the Subject does not have a smartphone the Sponsor can provide an Android tablet to help Subjects continuously track their postoperative outcomes in their natural environment, in real-time, and in a non-invasive manner. This type of patient direct data collection can improve data quality and method of collection and is potentially more sensitive to the changes in activities preoperatively compared to postoperatively (*e.g.*, not burdensome or possibly inconclusive like a paper diary).

Study sites and study Subjects are not required to join in the optional portion of the study.

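### Section 16.13 specifies no within-subject analysis for Hip Evaluation change or for ActiTrak pain before and after surgery

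*Combined protocol and SAP*

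**What the plan says.** Section 10.4 lists change in FJS-12, HOOS and Hip Evaluation as a tertiary endpoint that "will be measured and compared from preoperative to 6-weeks, 3-months, minimum 1-year and minimum 2-years". Section 16.13 repeats this almost unchanged: "will be measured and compared from preoperative to 6 weeks, 3 months, minimum 1 year and minimum 2 years".

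The methods in 16.13 then diverge by instrument. FJS-12 and HOOS get raw scores and change from baseline, with t-based intervals. For the third instrument, "Frequency tables will be provided for the following Hip Evaluation outcomes", with exact binomial 95% intervals; the items named are satisfaction, procedure again, and groin and buttock pain. No change estimate is described for it.

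For the optional activity tracking, 16.13 first leaves the method open: "The number of subjects participating, and the completeness and cleanliness of those data will impact analysis methods". It then sets a floor: "At minimum, pain level before and after surgery will be summarized and presented by the corresponding category". Section 10.6 describes who can contribute: "If a Subject is unable or unwilling to provide the preoperative data, this will not preclude or delay them from enrollment", and "Subjects may also enroll in the Patient Activity Tracking on the day of their surgery and collect activities through the 3-month postoperative visit interval". Section 16.5 restricts all analyses to data actually collected.

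**The concern.** A change endpoint asks how the same people moved between two visits. Two separate percentages with separate one-sample intervals do not answer that. They hide how many subjects improved and how many worsened, and they carry no interval for the difference. This is a gap for Hip Evaluation even if nobody is lost.

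ActiTrak adds a composition problem. Anyone who joins on the day of surgery can contribute only to the after side. If late joiners differ in postoperative pain from those who joined earlier, the after figure moves for reasons unrelated to change. At stake is whether before-after statements about groin pain, buttock pain and tracked pain can be read as change in the study's subjects.

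**Working it through.** **The plan's own figure.** Neither tertiary result has a stated figure. The only computed quantity in the plan is the margin of error in 16.9 (SD 10, about 200 THA subjects): 1.96 × 10 / √200 = 1.39, which agrees with the stated 1.4. The same inputs give the attrition used below: 1 − 200/225 = 11.1%, with 225 from 16.1 and 200 from 16.9.

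**Step 1. Hip Evaluation with complete follow-up.** Assume 200 subjects answer at both visits, with groin pain at 30% before and 20% after. At least two quite different histories fit those margins:

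- 10% improve and 0% become newly painful (discordant share d = 0.10);
- 30% improve and 20% become newly painful (d = 0.50).

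The difference is −10 points in both. The 95% half-width for the paired difference is 1.96 × √((d − 0.10²)/200):

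- d = 0.10: 1.96 × √(0.09/200) = 4.2 points;
- d = 0.50: 1.96 × √(0.49/200) = 9.7 points.

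The planned tables would be the same in both cases, so neither the within-subject picture nor the interval can be recovered from them.

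**Step 2. Composition effect, ActiTrak.** Let f be the share of trackers with preoperative data, and assume all of them also have postoperative data. Then:

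- unpaired shift = f × (after-rate, those with preoperative data) + (1 − f) × (after-rate, late joiners) − (before-rate, those with preoperative data);
- paired shift = (after-rate − before-rate), those with preoperative data;
- artefact = unpaired − paired = (1 − f) × (after-rate in late joiners − after-rate in those with preoperative data).

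The documents give neither f nor the gap. Absolute artefact, in percentage points, over an assumed range:

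| f | gap 10 | gap 20 | gap 30 |
|---|---|---|---|
| 90% | 1.0 | 2.0 | 3.0 |
| 75% | 2.5 | 5.0 | 7.5 |
| 50% | 5.0 | 10.0 | 15.0 |
| 25% | 7.5 | 15.0 | 22.5 |

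An illustration with no true change (all values assumed): 60 subjects with both values are at 70% in a pain category before and after, and 40 after-only subjects are at 50%. The before figure is 70%. The after figure is (60 × 70% + 40 × 50%)/100 = 62%. The 8-point apparent shift is composition alone.

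**Step 3. Composition effect, Hip Evaluation.** Here the after group is the subset, reduced by attrition m. The artefact is m × (preoperative rate in completers − preoperative rate in dropouts). With m = 25/225 and assumed gaps of 10, 20 and 30 points, it is 1.1, 2.2 and 3.3 points. It cannot exceed 11.1 points at that attrition.

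**Step 4. Comparison within the plan.** Section 16.12 specifies McNemar's test and a paired t-test for leg length discrepancy before and after surgery. Paired analysis is therefore already part of the plan; 16.13 does not extend it to these two results.

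**The case against.** The strongest reply is that the plan does not commit to unpaired tables. It is silent on pairing, and for ActiTrak it states a minimum and deliberately leaves the method open because participation was optional. That is right, and a reader who infers that the text fixes an unpaired analysis goes too far. What remains is that no paired analysis or both-values subset is specified, so the choice would be made after the data are seen.

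A reader might also infer that before and after come from different subjects. The documents do not support this. ActiTrak subjects with preoperative data would largely also be in the after group, and Hip Evaluation is scheduled for all Subjects preoperatively and at every follow-up visit (Sections 6 and 12.2). Willingness and ability to complete it is an inclusion criterion (9.4, no. 16). Late entry without preoperative data is described only for tracking, so that mechanism does not carry over to Hip Evaluation.

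It is tempting to add that the procedure-again item cannot have a preoperative answer. The form is in Appendix A, which is not in the text available here. Which items are asked at which visit, including groin and buttock pain, has to be confirmed from the eCRF.

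Finally, both results are tertiary, and 16.3 calls all analyses exploratory. That stands and limits the consequence.

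**Conclusion.** The point holds as a minor one. For Hip Evaluation, the declared endpoint is change and the specified analysis cannot deliver it; this does not depend on attrition or on any assumed gap. Composition adds little there: about 1 to 3 points for assumed gaps of 10 to 30 points, if the attrition expected for the THA primary endpoint also applies to this form. For ActiTrak pain, the plan expressly allows after-only participants, and the possible artefact runs from 1 to 22.5 points over the assumed ranges. Where it would fall cannot be said, because participation and the share with preoperative data are not in the documents. No decision or sample size rests on either result, and the primary endpoint is unaffected.

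**What to change.** Amend 16.13, keeping the full frequency tables:

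1. For Hip Evaluation items answered preoperatively (groin and buttock pain, if the form asks them then), report at each visit the number with both values and the paired difference in proportions, post minus pre, with a 95% confidence interval.
2. For ActiTrak pain, add a pre-by-post category table in subjects with both values, and show post-only joiners separately.
3. In 10.4 and 16.13, limit the change wording to items with a preoperative answer. The sponsor should confirm from the eCRF whether the procedure-again item is postoperative only.

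The cost is SAP wording and some re-cut tables. No new data are needed: tracking has concluded (10.6), and Hip Evaluation is already scheduled before and after surgery. The drawback is a smaller n in the paired tables, which is why the full tables should stay beside them.
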